APPENDIX 7 – EQ-5D-5L QUESTIONNAIRE

Under each heading, please tick the ONE box that best describes your health TODAY.

MOBILITY

I have no problems in walking about
I have slight problems in walking about
I have moderate problems in walking about
I have severe problems in walking about
I am unable to walk about

SELF-CARE

I have no problems washing or dressing myself
I have slight problems washing or dressing myself
I have moderate problems washing or dressing myself
I have severe problems washing or dressing myself
I am unable to wash or dress myself

USUAL ACTIVITIES (e.g. work, study, housework, family or leisure activities)

I have no problems doing my usual activities
I have slight problems doing my usual activities
I have moderate problems doing my usual activities
I have severe problems doing my usual activities
I am unable to do my usual activities

PAIN / DISCOMFORT

[figure not shown]
I have no pain or discomfort
I have slight pain or discomfort
I have moderate pain or discomfort
I have severe pain or discomfort
I have extreme pain or discomfort

ANXIETY / DEPRESSION

I am not anxious or depressed
I am slightly anxious or depressed
I am moderately anxious or depressed
I am severely anxious or depressed
I am extremely anxious or depressed

- We would like to know how good or bad your health is TODAY.
- This scale is numbered from 0 to 100.
- 100 means the best health you can imagine.
0 means the worst health you can imagine.
- Mark an X on the scale to indicate how your health is TODAY.
- Now, please write the number you marked on the scale in the box below.

YOUR HEALTH TODAY =

APPENDIX 8 – KAROLINSKA SLEEPINESS SCALE

Here are some descriptors about how alert or sleepy you might be feeling right now. Please read the carefully and CIRCLE the number that best corresponds to the statement describing how you feel at the moment.

1. Extremely alert
2. Very Alert
3. Alert
4. Rather Alert
5. Neither alert nor sleepy
6. Some signs of sleepiness
7. Sleepy, but no difficulty remaining awake
8. Sleepy, with some effort to keep alert
9. Extremely sleepy, fighting sleep

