2.4 EXPLORATORY OBJECTIVE

Exploratory objectives of this study [Cohort 1 and 2 will be evaluated separately] include:

- The change from baseline in health and social care resource use including planned and unplanned hospital visits, use of ambulances, general practitioner (GP) visits, speech and language therapy utilization, occupational and physical therapy utilization.
- Change from baseline in sleep quality.

- Change from baseline in mealtime behavior.
- Effect of study medication on sleepiness (Karolinska Sleepiness Scale).
- Assessment of a Dravet syndrome composite endpoint including seizure frequency and severity and subjective patient-relevant outcome measures (eg, behavior, sleepiness, etc) using data from the collected rating scales will be performed.

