2.5.4 Exploratory Endpoints

The exploratory endpoints of the study are:

- Health and social care resource use including GP visits, speech and language, occupational and physical therapy, in addition to acute hospital and institutional length of stay, loss of work, etc.
- Change in sleep quality assessed by the patient/caregiver
- Change in mealtime behavior assessed by the patient/caregiver
- Sleepiness assessed by the patient/caregiver using the Karolinska Sleepiness Scale
- Composites endpoints that combine objective and subjective measures

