6.2.5.6 Clinic Visit 8 (Maintenance Period: Day 50)

Subjects will report to the clinic in the morning on Maintenance Period Day 50. Subjects should not take their morning dose(s) of study medication and AED medication prior to reporting to the clinic. The following procedures will be performed:

- Review current seizure activity (number/type/duration) from diary since previous visit
- Record concomitant medications
- Abbreviated physical examination, including height and weight, and calculation of BMI
(Note: if the subject's weight is $\pm 25\%$ of the weight at Day -1, the IMP dose will be recalculated)
- Vital signs (blood pressure, heart rate, temperature, and respiratory rate)
- 12-lead ECG
- Doppler ECHO (this must be obtained any time between Day 40 and Day 54)
- Urine pregnancy test for females of child-bearing potential
- Laboratory evaluation (serum chemistry and hematology, and urinalysis)
- Urine THC panel
- Whole blood CBD
- Collect plasma sample for background AED PK evaluation prior to the morning dose of study medication(s)
- Collect and review diary with parent/caregiver
- Dispense diary
- C-SSRS Children's Since Last Visit Assessment ([Appendix 2](#))
- PedsQL Generic Core Scale ([Appendix 6](#))
- BRIEF ([Appendix 3](#))
- QOLCE ([Appendix 4](#))
- PedsQL Family Impact Module ([Appendix 6](#))
- CGI-I (assessed by parent/caregiver)

- CGI-I (assessed by investigator)
- Administer sleep quality and mealtime behavior questions
- Karolinska Sleepiness Scale ([Appendix 8](#))
- Record AEs
- Record AESI
- Collect used, partially used and unused study medication; perform drug accountability and review with parent/caregiver
- Dispense study medication

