7.1.4 Karolinska Sleepiness Scale (Exploratory Endpoint)

The Karolinska Sleepiness Scale ([Appendix 8](#)) will be administered according to the schedule in [Table 1](#) and [Table 2](#). The Karolinska Sleepiness scale is a self-report scale that measures the subject's drowsiness. It is a 9-point verbally anchored scale, which ranges from 'extremely

‘alert’ at one end of the scale to ‘extremely sleepy – fighting sleep’ at the other end of the scale. Within this study, the scale will be completed by the observer in an exploratory manner.

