6.3.4.3 Change from baseline on Karolinska Sleepiness Scale

The Karolinska Sleepiness Scale will be administered according to the schedule visit time points in [Table 1](#). The Karolinska Sleepiness scale is a self-report scale that measures the subject's drowsiness. It is a 9-point verbally anchored scale, which ranges from 'extremely alert' at one end of the scale to 'extremely sleepy – fighting sleep' at the other end of the scale. Within this study, the scale will be completed by the observer in an exploratory manner.

Score	Description
1	Extremely alert
2	Very alert
3	Alert
4	Rather alert
5	Neither alert nor sleepy
6	Some signs of sleepiness
7	Sleepy, but no effort to keep awake
8	Sleepy, some effort to keep awake

9

Very sleepy, great effort to keep awake, fighting sleep

Descriptive statistics will be presented for each time point where measured and will include number and percent of subjects in each category, mean, standard deviation, median, minimum and maximum. The ZX008 0.5 mg/kg/day and placebo groups will be compared on change from baseline using a Wilcoxon rank sum test.

Additionally, scores of 1-6 will be categorized as “Active” and scores of 7-9 categorized as “Sleepy”. These categorizations will be summarized using counts and percent (%) of subjects by treatment by each visit time point. A Fisher’s exact test will compare the proportion of subjects reporting sleepy scores (7, 8 or 9) in the ZX008 0.5 mg/kg/day to the analogous proportion in the placebo group.

All Karolinska Sleepiness data will be presented in the subject data listing.

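### The Karolinska form in Appendix 8 keeps its self-report wording although an observer is to rate the child, so some observers may rate themselves and blur the exploratory sleepiness comparison

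*Protocol*

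**What the plan says.** Protocol Appendix 8 reproduces the scale as a form addressed to the person holding it. It opens "Here are some descriptors about how alert or sleepy you might be feeling right now" and continues "Please read the carefully and CIRCLE the number that best corresponds to the statement describing how you feel at the moment". It mentions neither a child nor a subject. The visit lists for Cohort 2 Visits 6, 8, 10 and 12 (Protocol 6.2.5) point to this appendix; the Visit 3 list names the scale without the reference.

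The intended construct is stated in the SAP: "The Karolinska Sleepiness scale is a self-report scale that measures the subject's drowsiness". Protocol 7.1.4 agrees, and adds: "Within this study, the scale will be completed by the observer in an exploratory manner". SAP 6.3.4.3 repeats that sentence. Protocol 2.5.4 describes the rater differently: "Sleepiness assessed by the patient/caregiver using the Karolinska Sleepiness Scale".

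SAP 6.3.4.3 plans two arm comparisons. The first is on the score: "The ZX008 0.5 mg/kg/day and placebo groups will be compared on change from baseline using a Wilcoxon rank sum test". The second is a Fisher's exact test on the proportion scoring 7, 8 or 9, which the SAP labels sleepy. Both are exploratory and lie outside the hierarchy in SAP 6.1.2.

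**The concern.** The plan wants a proxy rating of the child, but the form asks for a self-rating. Neither document contains an adapted stem or tells the observer to answer about the child. If some observers answer about themselves, the analysis mixes ratings of two different people, and nothing in the planned data would separate them.

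What is at stake is how a null result would be read. The effect of study medication on sleepiness is a listed exploratory objective (Protocol 2.4). SAP 6.4.1.2 rules out p-values for adverse events, so these two tests are the only formal arm comparisons of a measure dedicated to sleepiness. Sleepiness is also named as an example component of the planned Dravet composite (Protocol 2.4), so misdirected ratings could carry over there.

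**Working it through.** The plan gives no figure for this endpoint to reproduce. The main check is a comparison of texts.

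**Who is to be rated, and by whom**

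| Source | Person rated | Rater |
|---|---|---|
| Protocol 7.1.4 | subject | observer |
| SAP 6.3.4.3 | subject | observer |
| Protocol 2.5.4 | not stated | patient/caregiver |
| Protocol Appendix 8 | whoever reads the form | whoever reads the form |

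The last row agrees with the first two only if the rater is also the subject, and those two rows say that an observer completes the scale.

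**How the other caregiver forms address their reader**

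- Forms about the subject refer to the child: QOLCE (Appendix 4), the BRIEF parent form (Appendix 3), the PedsQL Generic Core parent reports (Appendix 6, with the teen version saying teen), and the sleep and mealtime questions (7.1.3).
- Forms that ask about *you* concern the caregiver: EQ-5D-5L (Appendix 7) and the PedsQL Family Impact Module (Appendix 6), which includes items on the caregiver's own tiredness.
- In Cohort 2 the Family Impact Module is given at Visits 3, 8 and 12 and EQ-5D-5L at Visits 3 and 12. The Karolinska scale is given at all of these.

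Under the trial's own convention, an unqualified *you* refers to the caregiver. A literal reading of the Karolinska form is therefore a realistic risk.

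**Could the subject be the reader?** Subjects are aged 2 to 18 (4.1), at least 40% are planned to be under 6 (3.1), and cognitive impairment is part of the syndrome (1.1). Some subjects may be able to answer; many will not.

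**Anchors.** All three levels that define sleepy in the Fisher test differ between the form and the SAP:

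| Level | Appendix 8 | SAP 6.3.4.3 |
|---|---|---|
| 7 | staying awake is not difficult | no effort is made to stay awake |
| 8 | some effort, to stay alert | some effort, to stay awake |
| 9 | extreme sleepiness | very sleepy, with great effort to stay awake added |

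**Illustration of dilution.** Let q be the fraction of observers who rate themselves, and assume that their own sleepiness does not differ by arm. Then

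observed mean difference = (1 − q) × true mean difference.

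Take the protocol's 45 per arm (10.1), a two-sided alpha of 0.05 and a two-sample t-test as a stand-in for the Wilcoxon test. The true difference of 1 point, the SD (held constant over q) and q are all assumptions; none comes from the documents.

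| Assumed SD | q = 0 | q = 25% | q = 50% |
|---|---|---|---|
| 1.5 | 88% | 65% | 35% |
| 2.0 | 65% | 42% | 22% |
| 2.5 | 47% | 29% | 16% |

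At q = 0 nothing is lost. At q = 100% the expected difference is zero and the comparison says nothing about the child. The table shows how sensitive the comparison is; it does not forecast the loss.

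The assumption that caregiver sleepiness is unrelated to arm could fail. If caregivers become less tired because the child improves, self-ratings would move against a sedation signal instead of only diluting it. This is why dilution is probable and not certain.

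**The case against.** The strongest reply is that the intent is not in doubt. Protocol 7.1.4 and SAP 6.3.4.3 both say that the scale measures the subject's drowsiness through an observer. A trained site would probably explain this, and many caregivers would answer about the child whatever the stem says. This has force. A reader might infer that the comparison will consist of caregivers' own ratings, but that is only the q = 100% case, and the documents give no value for q. Because the rater is named as observer in two places and patient/caregiver in another, it is also not settled that a caregiver always completes the form. Where a capable patient does, the wording fits.

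A second reply is that sedation has other routes into the data. Adverse events are tabulated by preferred term and arm (SAP 6.4.1.2). The QOLCE has an Energy/Fatigue subscale, with change compared by a Wilcoxon test (SAP 6.3.3.10). PedsQL has an energy item. So the documents do not support the inference that a sedating effect would go unseen.

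A third tempting reading is that ratings are taken when the drug effect is lowest, because the Visit 8 instruction says "Subjects should not take their morning dose(s) of study medication and AED medication prior to reporting". The documents do not support this. No section fixes whether the scale is completed before or after the in-clinic dose, and both arms follow the same instructions at each visit, so differences between visits do not bias the arm comparison.

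Finally, the protocol makes no power claim for this endpoint. That is correct, and the illustration should not be read as a shortfall against a target. None of these replies supplies the missing observer wording.

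**Conclusion.** The point holds as a wording defect with an uncertain effect. The printed form, followed literally, rates the wrong person; nothing in either document corrects it; and the rater is named inconsistently. Some dilution of the exploratory sleepiness comparison is probable, by an amount that cannot be derived from the documents. The direction rests on the assumption that caregivers' own sleepiness does not depend on arm.

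The primary endpoint, both key secondary endpoints and the type I error control are unaffected. The difference in anchors is a separate, smaller inconsistency that bears on what the Fisher cut means. The reason to act is that the correction is very cheap and, without it, a finding of no difference in sleepiness would be hard to interpret.

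**What to change.** 1. Reword the Appendix 8 stem so that the observer rates the child, for example: *how alert or sleepy your child appears right now*. Keep the momentary time frame. Moving to a recall period such as the past week would change the scale in a further, debatable way and is not needed to solve this problem.
2. Name the same rater in Protocol 2.5.4, Protocol 7.1.4 and SAP 6.3.4.3.
3. Use the Appendix 8 anchors for levels 7 to 9 in SAP 6.3.4.3, so that the Fisher cut refers to what respondents actually read.
4. For ratings already taken on the self-worded form, record who was rated where this can be established. Add a sensitivity analysis that omits those shown to be self-ratings by the caregiver. Do not exclude all earlier ratings: that would discard valid proxy ratings, and subjects who lose their baseline would drop out of the change-from-baseline test.

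The cost is a revised and retranslated one-item form, small text edits in both documents, a query to sites and one added sensitivity analysis. The rewording departs from the self-report original, but the plan already does so by using an observer.

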APPENDIX 9 – MAXIMUM ALLOWABLE BLOOD DRAW VOLUMES

Maximum allowable blood draw volumes:

PATIENT'S WEIGHT		TOTAL VOLUME	MAXIMUM mL IN ONE BLOOD DRAW	MAXIMUM mL IN A 30-DAY PERIOD
Kg	lbs	mL		
1	2.2	100	2.5	5
2	4.4	200	5	10
3	3.3	240	6	12
4	8.8	320	8	16
5	11	400	10	20
6	13.2	480	12	24
7	15.4	560	14	28
8	17.6	640	16	32
9	19.8	720	18	36
10	22	800	20	40
11 thru 15	24 thru 33	880-1200	22-30	44-60
16 thru 20	35 thru 44	1280-1600	32-40	64-80
21 thru 25	46 thru 55	1680-2000	42-50	64-100
26 thru 30	57 thru 66	2080-2400	52-60	104-120
31 thru 35	68 thru 77	2480-2800	62-70	124-140
36 thru 40	79 thru 88	2880-3200	72-80	144-160
41 thru 45	90 thru 99	3280-3600	82-90	164-180
46 thru 50	101 thru 110	3680-4000	92-100	184-200
51 thru 55	112 thru 121	4080-4400	102-110	204-220
56 thru 60	123 thru 132	4480-4800	112-120	224-240
61 thru 65	134 thru 143	4880-5200	122-130	244-260
66 thru 70	145 thru 154	5280-5600	132-140	264-280
71 thru 75	156 thru 165	5680-6000	142-150	284-300
76 thru 80	167 thru 176	6080-6400	152-160	304-360
81 thru 85	178 thru 187	6480-6800	162-170	324-340
86 thru 90	188 thru 198	6880-7200	172-180	344-360
91 thru 95	200 thru 209	7280-7600	182-190	364-380
96 thru 100	211 thru 220	7680-8000	192-200	384-400

Based on blood volume of:

1 to 2 kg 100 mL/kg (pre-term infant)
>2 kg 80 mL/kg (term infant - adult)

This information is similar to that used by the Committee on Clinical Investigations at Children's Hospital in Los Angeles, and at Baylor College of Medicine in Dallas, TX.

Adapted by [name]. August 2001
Children's Hospital and Regional Medical Center Laboratory
Seattle, WA

APPENDIX 10 – SUMMARY OF PROTOCOL AMENDMENT 2.3.83.3

Summary of Changes from Amendment 2.3.8 to Amendment 3.3 of the protocol.

The protocol amendment number was updated to Amendment 3.3, 2 February 2018.

Rationale: Increase n of Cohort 2 based on results from Study 1 which show that the SD can range between 50% and 69%.	
Original Text	Amendment Text
Synopsis and Section 3.2, 4.7 
Approximately 85 subjects will be screened to obtain 80 subjects who enter the Baseline Period. Of these 80 subjects, it is estimated that at least 70 subjects will be randomized into the Titration Period.
	Synopsis and Section 3.2, 4.7 
Approximately 115 subjects will be screened to obtain 80 subjects who enter the Baseline Period. Of these 80 subjects, it is estimated that at least 70 subjects will be randomized into the Titration Period.

Synopsis and Section 3.2 
Approximately 25 subjects will be screened to ensure 20 subjects enter the study and complete all PK assessments. Subjects who discontinue prior to completion of all study-related procedures may be replaced.
	Synopsis and Section 3.2 
Approximately 25 subjects will be screened to ensure 18-20 subjects enter the study and complete all PK assessments. Subjects who discontinue prior to completion of all study-related procedures may be replaced.

Rationale: Increase n of Cohort 2 based on results from Study 1 which show that the SD can range between 50% and 69%.	
Original Text	Amendment Text
Synopsis and Section 10.1: 
The sample size for Cohort 2 is based on results from the only randomized, placebo-controlled studies in subjects with Dravet syndrome can be found in the European Public Assessment Report (EPAR) for STP (EMA 2007). The EPAR summarizes the results from two studies: STICLO France and STICLO Italy. In the STP groups, the standard deviation (SD) of the percentage change in seizure frequency from baseline to Month 2 was 42% in the French trial and 26% in the Italian trial. The analogous SDs for placebo groups were 38% and 62%. An SD of 50% was assumed for the primary analysis in this trial comparing ZX008 to placebo on the change from baseline in seizure frequency. Using a two-sided test at the $\alpha=0.05$ significance level, a sample size of 35 subjects per treatment group affords 90% power to detect a difference in mean change from baseline of 40 percentage points. Thus, the total sample size for Cohort 2 is planned to be 70 subjects (35 per arm).
	Synopsis and Section 10.1: 
The sample size for Cohort 2 is based on results from Study 1, the only randomized, placebo-controlled study in subjects with Dravet syndrome sponsored by Zogenix (Lagae 2017). can be found in the European Public Assessment Report (EPAR) for STP (EMA 2007). The EPAR summarizes the results from two studies: STICLO France and STICLO Italy. In the STP groups, the standard deviation (SD) of the percentage change in seizure frequency from baseline to Month 2 was 42% in the French trial and 26% in the Italian trial. The analogous SDs for placebo groups were 38% and 62%. An SD of 50% was assumed for the primary analysis in this trial comparing ZX008 to placebo on the change from baseline in seizure frequency. U the end of study (Day 99) was 50% for the 0.8 mg/kg/day group and 69% for the 0.2 mg/kg/day group. For the sample size calculation for Cohort 2, the SD is assumed to be intermediate between the SDs observed in the high and low dose groups in Study 1. Assuming an SD of 58 and using a two-sided test at the $\alpha=0.05$ significance level, a sample size of 3545 subjects per treatment group affords 90% power to detect a difference in mean change in

	
seizure frequency from baseline of 40 percentage points. Thus, the total sample size for Cohort 2 is planned to be 70approximately 90 subjects (35/45 per arm).

Synopsis and Section 10.1: The 20 subjects targeted for the PK phase of the study is expected to be sufficient to allow for the extension of the PK information gained in the ongoing PK study in adults and existing PBPK models to pediatric patients with Dravet syndrome.	Synopsis and Section 10.1: The 18-20 subjects targeted for the PK phase of the study is expected to be sufficient to allow for the extension of the PK information gained in the ongoing PK study in adults and existing PBPK models to pediatric patients with Dravet syndrome.

Rationale: Updating Statistical Analysis and efficacy objectives to align with Statistical Analysis Plan: Moving CGI from exploratory to secondary objectives, removing 40% decrease in seizure frequency and adding 50% decrease in seizure frequency to secondary objectives
	
Original Text	Amendment Text
Synopsis and Section 2.2 The key secondary efficacy objectives of the study are related to Cohort 2 and include: 
○ To demonstrate that ZX008 is superior to placebo on the following endpoints:
- The proportion of subjects who achieve a \geq 40% reduction from baseline in convulsive seizure frequency.- The proportion of subjects who achieve a \geq 50% reduction from baseline in convulsive seizure frequency.- The longest convulsive seizure-free interval.	Synopsis and Section 2.2 The key secondary efficacy objectives of the study are related to Cohort 2 and include: 
○ To demonstrate that ZX008 is superior to placebo on the following endpoints:
— The proportion of subjects who achieve a \geq 40% reduction from baseline in convulsive seizure frequency.— The proportion of subjects who achieve a \geq 50% reduction from baseline in convulsive seizure frequency.— The longest convulsive seizure-free interval.

Synopsis and Section 2.3 Additional secondary efficacy objectives of the study (Cohort 2) are: 
○ To demonstrate that ZX008 is superior to placebo on the following endpoints:
- The number of convulsive seizure-free days.- The proportion of subjects who achieve \geq 75% reductions from baseline in convulsive seizure frequency.- The change from baseline in non-convulsive seizure frequency.- The change from baseline in convulsive + non-convulsive seizure frequency.- The incidence of rescue medication usage.- The incidence of hospitalization to treat seizures.- The incidence of status epilepticus (SE).- The change from baseline in health-related quality of life (HRQOL) measured using the Pediatric Quality of Life Inventory™ (PedsQL) Generic Core Scale.- The change from baseline in PedsQL Family Impact module score.- Change from baseline in subjects' quality of life measured using the Quality of Life in Childhood Epilepsy (QOLCE)- The change from baseline in the HRQOL of the parent/caregiver using the standardized measure of health status (EQ-5D-5L) scale.- The change from baseline on the impacts of the condition on parents and the family using the PedsQL family impact module.	Synopsis and Section 2.3 Additional secondary efficacy objectives of the study (Cohort 2) are: 
○ To demonstrate that ZX008 is superior to placebo on the following endpoints:
- The number of convulsive seizure-free days.- The proportion of subjects who achieve \geq 25% or \geq 75% reductions from baseline in convulsive seizure frequency.- The change from baseline in non-convulsive seizure frequency.- The change from baseline in convulsive + non-convulsive seizure frequency.- The incidence of rescue medication usage.- The incidence of hospitalization to treat seizures.- The incidence of status epilepticus (SE).- The change from baseline in health-related quality of life (HRQOL) measured using the Pediatric Quality of Life Inventory™ (PedsQL) Generic Core Scale.- The change from baseline in PedsQL Family Impact module score.- Change from baseline in subjects' quality of life measured using the Quality of Life in Childhood Epilepsy (QOLCE)- The change from baseline in the HRQOL of the parent/caregiver using the standardized measure of health status (EQ-5D-5L) scale.- The change from baseline on the impacts of the condition on parents and the family using the PedsQL family impact module.- Clinical Global Impression – Improvement (CGI-I) rating, as assessed by the principal investigator.- CGI-I rating, as assessed by the parent/caregiver.
Synopsis and Section 2.4 Exploratory objectives of this study (Cohort 2) include: 
- To assess the change from baseline in health and social care resource use. These measures include planned and unplanned hospital visits, use of ambulances, general practitioner (GP) visits, speech and language therapy utilization, occupational and physical therapy utilization.- Clinical Global Impression – Improvement (CGI-I) rating, as assessed by the principal investigator.	Synopsis and Section 2.4 Exploratory objectives of this study (Cohort 2) include: 
- To assess the change from baseline in health and social care resource use. These measures include planned and unplanned hospital visits, use of ambulances, general practitioner (GP) visits, speech and language therapy utilization, occupational and physical therapy utilization.- Clinical Global Impression – Improvement (CGI-I) rating, as assessed by the principal investigator.

- CGI-I rating, as assessed by the parent/caregiver.- Change from baseline in sleep quality.- Change from baseline in mealtime behavior.	
- CGI I rating, as assessed by the parent/caregiver.- Change from baseline in sleep quality.- Change from baseline in mealtime behavior.

Section 10.5.1.1 Primary Efficacy Analysis – Cohort 2
 
The first key secondary endpoint – the proportion of subjects who achieve a $\geq 40\%$ reduction from baseline in convulsive seizure frequency – is derived directly from the primary endpoint. That is, the proportion of subjects in the ZX008 group who have a change in convulsive frequency of at least 40 percentage points will be compared to the analogous proportion in the placebo group. The comparison will be made using a logistic regression model that incorporates the same factors and covariates as the ANCOVA used in the primary analysis. The second secondary endpoint, the proportion achieving a $> 50\%$ reduction in convulsive seizures, will be analyzed similarly. The analyses will be performed using data collected over the T + M period.
 
The longest interval between convulsive seizures will be calculated for each subject over the entire T + M period. The ZX008 and placebo groups will be compared using a log rank test.
	
Section 10.5.1.1 Primary Efficacy Analysis – Cohort 2
 
The first key secondary endpoint – the proportion of subjects who achieve a $\geq 50\%$ reduction from baseline in convulsive seizure frequency – is derived directly from the primary endpoint. That is, the proportion of subjects in the ZX008 group who have a change in convulsive frequency of at least 50 percentage points will be compared to the analogous proportion in the placebo group. The comparison will be made using a logistic regression model that incorporates the same factors and covariates as the ANCOVA used in the primary analysis. The second secondary endpoint, the proportion achieving a $> 50\%$ reduction in convulsive seizures, will be analyzed similarly. The analyses will be performed using data collected over the T + M period.
 
The longest interval between convulsive seizures will be calculated for each subject over the entire T + M period. The ZX008 and placebo groups will be compared using a Wilcoxon test.


Section 10.4.1.3 Multiplicity Strategy and Testing Hierarchy – Cohort 2
 
The efficacy analyses will employ a serial gatekeeper strategy to maintain the Type 1 error rate at $\alpha=0.05$ across the family of analyses that support the primary and key secondary objectives. The strategy specifies a hierarchy of significance tests where each test acts as a gatekeeper to the tests below it.
 
The primary and key secondary endpoints will be assessed in the following order entailing comparisons between the ZX008 and placebo groups on
 
• The change in MCSF from baseline.• The proportion of subjects who achieve a $\geq 40\%$ reduction from baseline in convulsive seizure frequency.	
Section 10.4.1.3 Multiplicity Strategy and Testing Hierarchy – Cohort 2
 
The efficacy analyses will employ a serial gatekeeper strategy to maintain the Type 1 error rate at $\alpha=0.05$ across the family of analyses that support the primary and key secondary objectives. The strategy specifies a hierarchy of significance tests where each test acts as a gatekeeper to the tests below it.
 
The primary and key secondary endpoints will be assessed in the following order entailing comparisons between the ZX008 and placebo groups on
 
• The change in MCSF from baseline.• The proportion of subjects who achieve a $\geq 40\%$ reduction from baseline in convulsive seizure frequency.

• The proportion of subjects who achieve a $\geq 50\%$ reduction from baseline in convulsive seizure frequency.• The longest convulsive seizure-free interval.	
• The proportion of subjects who achieve a $\geq 50\%$ reduction from baseline in convulsive seizure frequency.• The longest convulsive seizure-free interval.								
Section 10.5.2 Safety Analyses Hematology and chemistry laboratory results for subjects in Cohort 2 will be summarized using shift tables that tabulate the proportion of subjects who have lab results that change from baseline. Shift tables will be presented for each time point where lab results are collected by descriptive statistics at each time point available. Mean change from baseline will also be calculated for continuous hematology and chemistry results at all time points available.	Section 10.5.2 Safety Analyses Hematology and chemistry laboratory results for subjects in Cohort 2 will be summarized using shift tables that tabulate the proportion of subjects who have lab results that change from baseline. Shift tables will be presented for each time point where lab results are collected by descriptive statistics at each time point available. Mean change from baseline will also be calculated for continuous hematology and chemistry results at all time points available.								
Rationale: Updates to Table 15, Adverse Events of Special Interest									
Original Text	Amendment Text								
Table 14 Adverse Events of Special Interest 

CV/Respiratory	

1. Chest pain – any pain in sternal area that is described for example as crushing, burning, sharp, stabbing or dull.	

2. Dyspnea/shortness of breath – any signs of difficult or labored breathing unrelated to a previous medical condition that has not worsened.	

3. Persistent cough – longer than 4 weeks without a confirmed identified pathogen (or any other persistent cough that the investigator feels is suspicious).	

	CV/Respiratory	1. Chest pain – any pain in sternal area that is described for example as crushing, burning, sharp, stabbing or dull.	2. Dyspnea/shortness of breath – any signs of difficult or labored breathing unrelated to a previous medical condition that has not worsened.	3. Persistent cough – longer than 4 weeks without a confirmed identified pathogen (or any other persistent cough that the investigator feels is suspicious).	Table 14 Adverse Events of Special Interest 

CV/Respiratory	

1. Chest pain – any pain in sternal area that is described for example as crushing, burning, sharp, stabbing or dull.	

2. Dyspnea/shortness of breath – any signs of difficult or labored breathing unrelated to a previous medical condition that has not worsened.	

3. Persistent cough – longer than 4 weeks without a confirmed identified pathogen (or any other persistent cough that the investigator feels is suspicious).	

	CV/Respiratory	1. Chest pain – any pain in sternal area that is described for example as crushing, burning, sharp, stabbing or dull.	2. Dyspnea/shortness of breath – any signs of difficult or labored breathing unrelated to a previous medical condition that has not worsened.	3. Persistent cough – longer than 4 weeks without a confirmed identified pathogen (or any other persistent cough that the investigator feels is suspicious).
CV/Respiratory									
1. Chest pain – any pain in sternal area that is described for example as crushing, burning, sharp, stabbing or dull.									
2. Dyspnea/shortness of breath – any signs of difficult or labored breathing unrelated to a previous medical condition that has not worsened.									
3. Persistent cough – longer than 4 weeks without a confirmed identified pathogen (or any other persistent cough that the investigator feels is suspicious).									
CV/Respiratory									
1. Chest pain – any pain in sternal area that is described for example as crushing, burning, sharp, stabbing or dull.									
2. Dyspnea/shortness of breath – any signs of difficult or labored breathing unrelated to a previous medical condition that has not worsened.									
3. Persistent cough – longer than 4 weeks without a confirmed identified pathogen (or any other persistent cough that the investigator feels is suspicious).									

4. Increase in blood pressure $>30\%$ from Screening blood pressure or systolic pressure ≥ 140 mmHg or diastolic pressure ≥ 90 mmHg after repeated measures during one visit (Only if the repeat measures in triplicate confirm the finding, and in the Investigator's opinion the finding is not due to the subject's agitation or non-cooperation, should this be reported as an AESI). Blood pressure should be repeated at appropriate times within the visit.	4. Increase in blood pressure $>30\%$ from Screening blood pressure or systolic pressure ≥ 140 mmHg or diastolic pressure ≥ 90 mmHg after repeated measures during one visit (Only if the repeat measures in triplicate confirm the finding, and in the Investigator's opinion the finding is not due to the subject's agitation or non-cooperation, should this be reported as an AESI). Blood pressure should be repeated at appropriate times within the visit.
5. New onset heart murmur	5. New onset heart murmur
6. Tachycardia – a persistent HR $>30\%$ above the screening value and unrelated to exercise, exertion or anxiety. (Only if the repeat measures in triplicate confirm the finding, and in the Investigator's opinion the finding is not due to the subject's agitation or non-cooperation, should this be reported as an AESI). Heart rate should be repeated at appropriate times within the visit.	6. Tachycardia – a persistent HR $>30\%$ above the screening value and unrelated to exercise, exertion or anxiety. (Only if the repeat measures in triplicate confirm the finding, and in the Investigator's opinion the finding is not due to the subject's agitation or non-cooperation, should this be reported as an AESI). Heart rate should be repeated at appropriate times within the visit.
7. Bradycardia – a persistent HR <50 bpm. (Only if the repeat measures in triplicate confirm the finding, and in the Investigator's opinion the finding is not due to the subject's agitation or non-cooperation, should this be reported as an AESI). Heart rate should be repeated at appropriate times within the visit.	7. Bradycardia – a persistent HR <50 bpm. (Only if the repeat measures in triplicate confirm the finding, and in the Investigator's opinion the finding is not due to the subject's agitation or non-cooperation, should this be reported as an AESI). Heart rate should be repeated at appropriate times within the visit.
8. Signs that could indicate right ventricular failure: 
 Peripheral edema Ascites Syncope Decompensated right ventricular failure – symptoms include shortness of breath, frequent coughing especially when lying flat, abdominal swelling and pain, dizziness, fainting, and fatigue	8. Signs that could indicate right ventricular failure: 
 Peripheral edema Ascites Syncope Decompensated right ventricular failure – symptoms include shortness of breath, frequent coughing especially when lying flat, abdominal swelling and pain, dizziness, fainting, and fatigue

9. Signs on ECHO indicative of potential valvulopathy (≤ 18 years of age)
 
  Valve regurgitation (aortic or mitral)  Moderate or severe valve regurgitation (tricuspid or pulmonary)  Mean Mitral valve gradient ≥ 4 mmHg  Mean Aortic valve gradient ≥ 15 mmHg  Mean Tricuspid valve gradient ≥ 4 mmHg  Peak Pulmonary valve gradient ≥ 21 mmHg 	
9. Signs on ECHO indicative of potential valvulopathy (≤ 18 years of age)
 
  Valve regurgitation (aortic or mitral)  Moderate or severe valve regurgitation (tricuspid or pulmonary)  Mean Mitral valve gradient ≥ 4 mmHg  Mean Aortic valve gradient ≥ 15 mmHg  Mean Tricuspid valve gradient ≥ 4 mmHg  Peak Pulmonary valve gradient ≥ 21 mmHg
